The SEER-Medicare database is composed of 2 large population-based sources of data that provide detailed information about Medicare beneficiaries with cancer: (1) the SEER registry data that contain information about an incident cancer diagnosis and (2) linked Medicare data that contain longitudinal information on Medicare enrollment and

specific healthcare services received in different settings (e.g., hospitals, physician offices, outpatient clinics, nursing homes), as well as prescription drug utilization. The linkage of these 2 data sources results in a unique source of information that can be used for an array of epidemiological research, including health services use and survival outcomes, among older patients with cancer in the United States (US) Medicare population.

The SEER registries are part of the SEER Program, which is an epidemiologic surveillance system consisting of population-based tumor registries in certain states and metropolitan areas designed to track cancer incidence and survival in the US. The SEER registries collect information on nearly all (98%) newly diagnosed cancer cases, including breast cancer, in persons residing in SEER areas. SEER areas have been shown to be nationally representative (Nattinger et al., 1997) and the 21 registries represented in the SEER data linkage available for this study (SEER-21) capture over one-third (35%) of the total US population (Enewold et al., 2020). In contrast to the entire population of the US, the SEER Program encompasses a population that displays greater racial and ethnic diversity, along with a higher representation of individuals facing economic disadvantages (Enewold et al., 2020).

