4.1 FULL ANALYSIS SET

Inclusion Criteria

Patients must meet all of the following inclusion criteria to be eligible for inclusion in the study:

1. *De novo metastatic (stage IV) disease at initial breast cancer diagnosis during 2015-2019 (Howlader et al., 2018):*
 - *Incident breast cancer diagnosis will be identified using the SEER Site Recode 26000, which includes cases classified as “breast” according to the International Classification of Diseases for Oncology, 3rd Edition codes: C50.0-C50.9, excluding histology codes 9050-9055, 9140, and 9590-9992 (National Cancer Institute, 2023b).*
 - *Staging at diagnosis will be determined using criteria applicable during the specific period. Specifically, the American Joint Committee on Cancer (AJCC) staging 7th edition variable will be used to classify diagnoses in year 2015, the derived SEER combined stage group variable will be used to classify diagnoses in years 2016-2017, and the derived Extent of Disease (EOD) stage group variable will be used to classify diagnoses in years 2018-2019.*
2. *Age \geq 65 years at diagnosis*
3. *“Age” as the reason for Medicare entitlement*
4. *Breast cancer recorded as the first cancer (coded as tumor sequence “1”) or the only cancer (coded as tumor sequence “0”) confirming no evidence of another, previous primary cancer diagnosis.*
5. *HR+/HER2- molecular subtype at diagnosis, using the SEER breast subtype variable (defined according to ER/PR and HER2 status)*
6. *Initiated 1L systemic therapy with a CDK4/6 inhibitor + AI or AI alone*
 - *Subsequently, and differing from Goyal et al. (2023), to assess the primary objective, the study cohort will be restricted to patients initiating 1L therapy with palbociclib + AI or AI alone within 6 months of mBC diagnosis:*
 - *It is assumed that most patients will initiate a systemic treatment within a few months of the diagnosis, and those who did not receive treatment*

PFIZER CONFIDENTIAL

within 6 months may have meaningful unobserved characteristics that likely influenced their treatment decisions.

7. *To ensure complete data for identifying the 1L of therapy, patients will be required to have continuous enrollment in Medicare Parts A and B and have prescription drug coverage (Part D) with no HMO participation from date of diagnosis until they initiate the 1L therapy, and they are allowed up to 6 months to initiate first-line therapy.*

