8. *Continuously enrolled in Medicare Parts A and B with no HMO participation for ≥ 6 months before the index date*
 - *Because HMOs are not obligated to provide information about healthcare encounters (i.e., administrative procedure and diagnosis codes) to the Medicare system, patients who were enrolled in an HMO during study period may have incomplete data on service utilization, which may affect the accuracy of measurement for comorbid conditions and receipt of systemic therapy lines.*

Exclusion Criteria

Patients will be excluded if their mBC diagnosis was first recorded in a death certificate or at the time of autopsy.

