5.5 EXPOSURE VARIABLES AND COVARIATES

The exposure and other covariates to be analyzed as part of the study objectives and associated definitions are described in [Table 5-2](#). For covariates, categories may be further combined if appropriate for statistical purposes.

Table 5-2. Definitions of Exposure Variables

Variable	Role/objective	Definition
Exposure variables		
1L treatment type	Primary	
Patients initiating 1L therapy with one of the following regimens (to be identified in the Prescription Drug Event file using the generic drug names and HCPCS procedure codes, as applicable):
 
 • Palbociclib + AI • AI alone 
AI will include the following individual agents:
 
 • Anastrozole (HCPCS code: S0170) • Letrozole (HCPCS code: N/A) • Exemestane (HCPCS code: S0156) 
Therapy line definition: For each patient, the 1L therapy will be defined as all agents administered within a 60-day period after treatment initiation. The 1L therapy will start on the date the first agent will be

PFIZER CONFIDENTIAL

Variable	Role/objective	Definition
		administered (or filled) and will be considered to have ended upon occurrence of the earliest of any of the following: treatment switch to a new regimen or a gap of more than 90 days in administration or refill of any of the 1L regimen drugs. The start and end dates of the second and subsequent therapy lines will be defined in a similar fashion. The rules defining "treatment switch to a new regimen" are presented in Appendix 1.
Subsequent treatment	Exploratory	All subsequent treatment lines for patients initiating 1L therapy with palbociclib + AI or AI alone, including a description of treatment switch from AI alone to palbociclib + AI.
Control variables/covariates		
Tumor grade at diagnosis	Clinical characteristic (assessed at mBC diagnosis)	The tumor grade will be summarized as below: 
 • Grade 1 (lowest grade; well differentiated) • Grade 2 • Grade 3 • Grade unknown

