7.2 STATISTICAL ANALYSES

7.3 ANALYSES FOR PRIMARY OBJECTIVE

For the primary objective, the association between primary independent variable (treatment type: palbociclib + AI or AI alone) and the outcome variable (OS) will be assessed using unadjusted Kaplan-Meier analysis and multivariable methods. The primary method of analysis to account for observed confounders will be stabilized inverse probability of treatment weighting (sIPTW). Additionally, as sensitivity analyses, multivariable Cox proportional hazards (CPH) regression and propensity score matching (PSM) will be performed. *Both IPTW and PSM are propensity score (PS)-based methods commonly used to achieve balance between treatment and control groups in retrospective cohort study designs.* All methods are described below in detail.

Kaplan-Meier Analysis

Time-to-event outcome (i.e., OS) will be described using unadjusted Kaplan-Meier analyses; median time-to-event (in months) and landmark probabilities of event at various timepoints (e.g., 12 months, 24 months) will be estimated, along with 95% CIs and log-rank *P* values. Graphical displays of the data will also be generated as appropriate. Kaplan-Meier analysis may also be performed using the stabilized weights or among the PS-matched groups (see details in this section below), and the weighted or PS-matched survival curves may be drawn.

Cox Proportional Hazards Regression

The CPH regression model may be used to estimate a hazard ratio of the OS, along with 95% CI, for the primary exposure—a dichotomous variable indicating whether the patient received AI + palbociclib versus AI alone—and for each of the control variables included in the model, indicating higher or lower rate of death (relative to a reference category) at any given point in time after the index date. The patient demographic and clinical characteristics that will be considered for confounding adjustment in the model are described earlier in [Table 5-2](#).

Propensity Score Estimation

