As the first step in implementation of PS-based methods (IPTW and PSM), the PS (i.e., the estimated probability of treatment assignment) will be obtained from a logistic regression model where the treatment assignment (treatment vs. control) will be regressed on a set of covariates or confounders. The baseline covariates or control variables that will be considered for adjustment in the multivariable logistic regression for deriving treatment probabilities (i.e., PSs for IPTW and PSM) are described earlier in [Table 5-2](#). The following variables will be included in the model: age group, race, year of mBC diagnosis, marital status, geographic status of residence, median household income, LIS coverage, tumor grade at initial diagnosis, involvement of metastatic sites at initial diagnosis (bone, brain, liver, and lung as independent binary variables), and NCICI score category. If any covariates are identified to have missing data, they may be coded as “missing” or “unknown” and included as categorical variables in the model.

Covariate Balancing

The following process will be implemented to determine whether there is sufficient overlap between the patient populations of the 2 treatment cohorts:

- Compute the standardized mean difference in PS for each level of each baseline covariate
- Graphically assess differences in the full distribution of each covariate between 2 treatment cohorts
- An absolute standardized mean difference < 0.1 indicates negligible difference and is considered a good balance

Covariate balance will be examined using both IPTW and PSM techniques as described below. Subsequently, depending on the quality of balance, the endpoint (OS) may be assessed using one or both techniques (Austin, 2014; Buchanan et al., 2014).

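### Table 5-2 and the propensity score hold no local treatment given between diagnosis and index, so any arm difference in it that the listed covariates do not carry would stay in the OS hazard ratio unseen

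*SAP*

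**What the plan says.** SAP 5.5 states "The exposure and other covariates to be analyzed as part of the study objectives and associated definitions are described in" Table 5-2. The clinical entries there are tumour grade, metastatic sites at diagnosis, and the NCI comorbidity index (NCICI) over the 6 months before index. The other entries are age, year of diagnosis, race and ethnicity, marital status, region, income, low-income subsidy and Medicaid eligibility. No entry covers surgery of the primary tumour or radiotherapy. Protocol Table 1 has the same gap, and the agent list in SAP Appendix 2 is confined to systemic drugs.

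SAP 7.3 fixes the propensity model: "The following variables will be included in the model: age group, race, year of mBC diagnosis, marital status, geographic status of residence, median household income", then low-income subsidy, then "tumor grade at initial diagnosis, involvement of metastatic sites at initial diagnosis (bone, brain, liver, and lung as independent binary variables), and NCICI score category". Protocol 9.7.1 leaves the final variable list to the SAP, so this is the operative list for the primary analysis by stabilised weighting.

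On timing, inclusion criterion 7 in SAP 4.1 says of patients after diagnosis "and they are allowed up to 6 months to initiate first-line therapy". Criterion 8 requires Parts A and B without HMO membership for at least 6 months before index. SAP 2.1 describes the linked Medicare data as covering "specific healthcare services received in different settings (e.g., hospitals, physician offices, outpatient clinics, nursing homes), as well as prescription drug utilization", and adds that the claims show when a patient was treated and with what kind of treatment.

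**The concern.** The tumour covariates describe the disease on the day of diagnosis, but follow-up and the treatment contrast start at index. In between, some patients may have the primary tumour removed and some may be irradiated. Both events precede index, so they are possible confounders and not consequences of the first-line regimen. On general clinical reasoning, which the documents do not supply, surgery can mark operable disease in a fitter patient and radiotherapy can mark symptomatic disease. Either could also influence whether palbociclib is added to the AI.

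The comparison is not randomised, and SAP section 3 tests whether the hazard ratio is below 1. If local treatment differs between arms beyond what the listed covariates explain, part of the estimated effect would belong to it. A reader of the results could not tell, because the variable would not have been derived.

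**Working it through.** **Step 1. Would any planned analysis reveal it?**

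- Primary weighted Cox model (SAP 7.3): adjusts for the listed propensity covariates only.
- Balance check (SAP 7.3): standardised differences for the baseline covariates, so only for variables that were derived.
- Residual-imbalance step (SAP 7.3): optional, and it reaches the same variables.
- Propensity matching: uses the same score.
- Multivariable Cox model: draws its covariates from Table 5-2.
- Start within 3 months of diagnosis (SAP 7.6): optional. It shortens the interval but does not measure local treatment.

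None of these would show a difference in local treatment.

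**Step 2. Could it be derived?** Index falls at most 6 months after diagnosis, and the baseline window is the 6 months before index, so the window spans the whole interval. Criteria 7 and 8 together secure Parts A and B claims throughout it. NCICI is already taken from the same window.

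**Step 3. How large could the effect be?** The plan states no prevalence of local treatment, no event count and no power (Protocol 9.5), so there is no figure to reproduce. For an omitted yes/no baseline factor, the approximate multiplier on the hazard ratio is

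factor = [1 + p1(g − 1)] / [1 + p0(g − 1)]

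where p1 and p0 are the shares with local treatment on palbociclib + AI and on AI alone, and g is the hazard ratio of local treatment on death. All three are assumptions. The illustrative true hazard ratio of 0.76 is from the electronic-health-record study cited in SAP section 2.

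| p1 | p0 | g | Factor | True 0.76 becomes |
|---|---|---|---|---|
| 20% | 20% | any | 1.00 | 0.76 |
| 20% | 30% | 0.7 | 0.94/0.91 = 1.033 | 0.785 |
| 30% | 20% | 0.7 | 0.91/0.94 = 0.968 | 0.736 |
| 20% | 40% | 0.6 | 0.92/0.84 = 1.095 | 0.832 |
| 40% | 20% | 0.6 | 0.84/0.92 = 0.913 | 0.694 |

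If local treatment marks worse disease, the directions reverse. With g = 1.5, 20% v 30% gives 1.10/1.15 = 0.957 and 30% v 20% gives 1.15/1.10 = 1.045.

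**Step 4. Check by simulation.** Cox models were fitted to 60,000 simulated patients per scenario (control median 43.2 months, from the same cited study; censoring at 6 to 71 months; true hazard ratio 0.76). With local treatment omitted, the last four rows of the table gave 0.800, 0.740, 0.842 and 0.681. With it in the model they gave 0.772, 0.766, 0.761 and 0.749. Formula and simulation agree to within about 0.03.

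**Step 5. Allow for the other covariates.** For the primary analysis, the relevant shares are those left after weighting. If weighting on the listed covariates halved the gap (an assumption), 20% v 25% with g = 0.7 gives 0.94/0.925 = 1.016, and 20% v 30% with g = 0.6 gives 0.92/0.88 = 1.045.

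**The case against.** A reader might infer that the arms do differ in local treatment and that the hazard ratio is therefore biased, most likely towards 1 because operated patients would collect in the AI-alone arm. The documents support neither step. They report no local treatment by arm and do not say that it affects the choice of regimen. If fitter, operated patients were instead steered to palbociclib, the same reasoning would move the hazard ratio the other way.

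Second, much of what local treatment marks may already be in the model. Bone, brain, liver and lung involvement are separate terms, alongside grade, age group and NCICI category. Only the remainder matters, so the table in Step 3 is crude and probably an upper guide for its own inputs. This stands. It reduces the likely size without removing the gap, because a yes/no site indicator does not separate symptomatic from silent disease, or resected from unresected.

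Third, the SAP describes the claims in general terms and never names surgery or radiotherapy, so availability is a reasonable inference and not a stated fact. Protocol 9.9 already concedes unmeasured confounding, and its list of unobserved factors is given as examples. This also stands, but a general caveat about unobserved factors is no reason to leave out one that appears derivable.

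Fourth, a 3% shift is small beside the cited study's interval of 0.65 to 0.87 around 0.76 (0.65/0.76 = 0.86 and 0.87/0.76 = 1.14, or about 14% each way). That is fair for a 10-point gap. Unlike sampling error, however, the shift would not shrink with more patients.

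**Conclusion.** The omission is confirmed in Table 5-2, in the propensity list and in every planned alternative analysis. What follows is a possible confounder that is neither adjusted for nor checked, not a demonstrated bias. Its direction is unknown. Under assumed shares, and before allowing for the other covariates, its size is about 3% either way for a 10-point gap with g = 0.7, about 9 to 10% either way for a 20-point gap with g = 0.6, and nil if the arms are equal. The listed covariates would absorb some of that. The change is worth making before the final analysis, because it affects the primary weighting model of a non-randomised comparison and appears to need only data already held.

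**What to change.** Add two yes/no covariates to Table 5-2, both derived from claims between diagnosis and the day before index: surgery of the primary tumour, and radiotherapy. Stopping before index keeps them strictly baseline. Report each by arm with standardised differences before and after weighting, judged against the SAP's own limit of 0.1. Enter both in the SAP 7.3 propensity model, which also feeds the matching, and in the multivariable Cox model. If the claims prove unable to identify them, name the omission among the limitations.

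The cost is two procedure-code lists, two more model terms and some misclassification from claims coding. No new data source appears to be needed and no patient is lost.

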2.1 STUDY DESIGN

[figure not shown]
This study will encompass a retrospective cohort analysis using clinical and administrative claims data from the linked SEER-Medicare database (providing SEER data are available through 2019 and linked Medicare claims are available through 2020) for patients with diagnosis of HR+/HER2- mBC at initial presentation. The study will assess the rates of OS in patients 65 years or older with diagnosis of *de novo* mBC from 2015-2019 who initiated 1L systemic therapy with palbociclib + AI or AI alone following the first approval of palbociclib in February 2015. **Figure 2-1** presents a graphical schema of the study design (drawn for a hypothetical patient and not to scale).

Based on the study schema presented below, the following key study definitions will apply:

- **De novo mBC diagnosis date window:** From 1 February 2015 through 31 December 2019
- **Study index date:** The date of 1L treatment initiation with palbociclib + AI or AI alone after the *de novo* mBC diagnosis
- **Case selection window:** From 1 February 2015 through 30 June 2020 – for the date of 1L treatment initiation (study index date)

- **Baseline period:** The 6-month period before the study index date (to assess patient baseline demographic and clinical characteristics)
- **Study follow-up:** All patients will be followed from their study index date through the earliest of the following: death, disenrollment from Medicare Part A (hospital insurance), Part B (medical insurance), or Part D (prescription drug insurance), enrollment in a health maintenance organization (HMO) plan, or end of the study database (31 December 2020).
- **Overall study period:** From 1 August 2014 (to allow up to 6 months of look back period for any patient with index date in February 2015) through 31 December 2020 (accounting for a minimum 6 months of potential follow-up for any patient with index date in June 2020).

Figure 2-1. Study Design Schematic (Depiction for a Hypothetical Patient)

AI = aromatase inhibitor; HER2- = human epidermal growth factor receptor 2-negative; HR+ = hormone receptor-positive; mBC = metastatic breast cancer.

Note: Figure not drawn to scale.

Study Population

The study population will represent Medicare beneficiaries (men or women) with diagnosis of HR+/HER2- mBC at initial presentation (i.e., de novo), as identified in the SEER-Medicare database.

Data Source

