5.1 EFFICACY/EFFECTIVENESS ENDPOINT(S)

As the primary endpoint, OS will be defined as time in months from initiation of 1L therapy to death from any cause. For details on endpoint definition, please refer to [Table 5-1](#).

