5.4 STUDY ENDPOINTS

The endpoints or study outcomes to be analyzed for each study objective and the associated definitions are described in [Table 5-1](#).

Table 5-1. Definition of Endpoints

Variable	Role/objective	Definition
Overall survival in 1L	Primary	The time in months from initiation of 1L therapy (palbociclib + AI or AI alone) to all-cause death . Patients who did not die will be censored at the end of study follow-up as defined in Section 2.1 .
CCI		[REDACTED]

Variable	Role/objective	Definition
CCI		
Time to chemotherapy	Exploratory	Time in months from the study index date to first initiation of chemotherapy in any subsequent therapy lines. Patients who did not initiate chemotherapy treatment as of last follow-up will be censored at the end of the follow-up.

1L = first line; AI = aromatase inhibitor; CDK4/6 = cyclin-dependent kinase 4 and 6;

CCI

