PSM: In the PSM technique, each patient in the palbociclib +AI cohort will be matched to a patient in the AI alone cohort using a 1-to-1 matching with no replacement, using the nearest neighbor method to match by closest propensity scores (with a caliper of 0.01). As described above, median OS, landmark probabilities of event at various timepoints, and 95% CI for the matched cohorts will be assessed, and the hazard ratio will be assessed using the univariate CPH model. To plot survival functions and to test for differences between AI + palbociclib and AI alone, the Kaplan-Meier estimator will be used. Given the matched nature of the study cohorts, the CPH analysis will use a robust variance estimator to account for the clustering within paired sets.

All patients will be followed from the start of therapy line through the earliest of the following: death; disenrollment from Medicare Parts A, B, or D; enrollment in an HMO plan; or end of the study database (31 December 2020). Section 7.6 discusses potential sensitivity analyses (e.g., adjusting for subsequent treatments received).

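### To the extent that palbociclib fills follow the first AI fill, setting the arm over the 60 days after OS starts adds an immortal-time component favouring palbociclib, which no listed sensitivity analysis would reveal

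*SAP*

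**What the plan says.** **Time zero.** SAP 2.1 defines the index date as "The date of 1L treatment initiation with palbociclib + AI or AI alone". SAP 5.1 states that "OS will be defined as time in months from initiation of 1L therapy to death from any cause", and Table 5-1 repeats it as "time in months from initiation of 1L therapy (palbociclib + AI or AI alone) to all-cause death". Table 5-2, like Protocol Table 1, starts first-line therapy on the day of the first agent, not the day the regimen is complete. On follow-up, SAP 7.3 says "All patients will be followed from the start of therapy line through the earliest of the following: death; disenrollment from Medicare Parts" and then completes the list of end points. Protocol 9.1 and 9.7.1 agree.

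**Arm.** Under Table 5-2, "the 1L therapy will be defined as all agents administered within a 60-day period after treatment initiation". In SAP 7.3 the exposure in the Cox model is "a dichotomous variable indicating whether the patient received AI + palbociclib versus AI alone", so it is fixed from day 0. The footnotes to SAP Appendix 1 and Protocol Annex 2 explain that CDK4/6 inhibitors get the 60-day window because insurance cover can hold up supply.

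**Checks.** SAP 7.3 makes stabilized inverse probability weighting (sIPTW) primary, with multivariable Cox and propensity score matching (PSM) as sensitivity analyses. Its balance criterion reads: "An absolute standardized mean difference < 0.1 indicates negligible difference and is considered a good balance".

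**The concern.** The arm depends on what happens after the survival clock has started. Take two patients who start an AI with palbociclib on order. One dies on day 20 before the palbociclib fill and is an AI-alone death. The other fills on day 40 and enters palbociclib + AI from day 0, bringing 40 days in which a death could not have been counted in that arm. Both effects push the hazard ratio below 1, the direction of the superiority hypothesis in SAP section 3.

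This shift does not shrink as the cohort grows. The primary and all listed sensitivity analyses share it, so agreement among them would not show that it is absent.

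**Working it through.** The plan has no figure to reproduce: Protocol 9.5 gives no sample size, and neither document estimates this bias.

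**Inputs from the documents**
- AI-alone median OS of 43.2 months, from a real-world study cited in the SAP Introduction.
- Potential follow-up of 6 to 71 months: index dates from 1 February 2015 to 30 June 2020, data to 31 December 2020 (SAP 2.1).

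**Assumed inputs**
- True hazard ratio 1.00 and no confounding.
- Share intended for palbociclib at the first fill, p = 35% or 50%.
- Share of those filling late, q = 0, 10, 30 or 50%.
- Hazard in the first 60 days flat (k = 1) or tripled (k = 3).
- Censoring uniform over 6-71 months.

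**Hazard.** 60 days is 60/30.44 = 1.971 months. Setting S(43.2) = 0.5 gives h = ln 2 / [43.2 + (k − 1) × 1.971].
- k = 1: 0.6931/43.2 = 0.0160 per month. Dead by day 60: 1 − exp(−0.0160 × 1.971) = 3.1%.
- k = 3: 0.6931/47.142 = 0.0147 per month. Dead by day 60: 1 − exp(−3 × 0.0147 × 1.971) = 8.3%.

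**Arm rule.** An intended patient with delay u counts as palbociclib + AI from day 0 if alive at u, and otherwise as AI alone. With p = q = 50% and uniform delays, the average chance of dying before the fill is 1.56% (k = 1) or 4.22% (k = 3). Deaths moved to AI alone are therefore 0.25 × 1.56% = 0.39% or 0.25 × 4.22% = 1.06% of the cohort.

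**Apparent hazard ratio.** Solve the large-sample Cox score equation for b, with r and d the number at risk and deaths in each arm (P for palbociclib + AI, A for AI alone), and G the uncensored fraction:

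Σ G(t) { d_P(t) − [d_P(t) + d_A(t)] · r_P(t)eᵇ / [r_P(t)eᵇ + r_A(t)] } = 0

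| Delay (days) | p | Early hazard | 0% late | 10% | 30% | 50% |
|---|---|---|---|---|---|---|
| 0-60 | 35% | flat | 1.000 | 0.995 | 0.984 | 0.973 |
| 0-60 | 50% | flat | 1.000 | 0.993 | 0.979 | 0.965 |
| 0-60 | 35% | tripled | 1.000 | 0.986 | 0.958 | 0.931 |
| 0-60 | 50% | tripled | 1.000 | 0.982 | 0.946 | 0.912 |
| 0-30 | 50% | flat | 1.000 | 0.996 | 0.989 | 0.982 |
| 0-30 | 50% | tripled | 1.000 | 0.991 | 0.972 | 0.954 |
| 30-60 | 50% | flat | 1.000 | 0.989 | 0.969 | 0.948 |
| 30-60 | 50% | tripled | 1.000 | 0.973 | 0.921 | 0.871 |

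In this model a day-60 landmark, or palbociclib as a time-varying exposure, returns 1.000 in the 50%-late scenarios.

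**Does weighting remove it?** The propensity model uses characteristics fixed at or before the first fill: "The following variables will be included in the model: age group, race, year of mBC diagnosis, marital status", followed by further baseline items. A simulation of the planned sIPTW Cox model used 2 × 1,000,000 patients per scenario, assumed measured confounding and 0.5% per month enrolment censoring. With uniform 0-60 day delays and 10-50% late, it gave 0.995-0.961 (flat) and 0.982-0.905 (tripled). The largest weighted standardized mean difference was 0.0008, so the balance check passes while the shift remains.

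**Would any analysis in SAP 7.6 show it?**
- Multivariable Cox and PSM keep the same arm and day 0.
- The 3-month restriction limits the time from diagnosis to the first fill, not from AI to palbociclib.
- RPSFT acts on AI-alone patients who later take a CDK4/6 inhibitor. Late fillers within 60 days are already palbociclib + AI.
- Dropping the enrolment criteria changes only the end of follow-up.

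The landmark probabilities in SAP 7.3 are Kaplan-Meier estimates at times such as 12 and 24 months, not a landmark analysis.

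**The case against.** **The bias is conditional and may be small.** This stands. The footnotes show that delays are allowed for, not how often they occur. The lowest value, 0.871, needs four assumptions together: half intended, half of those late, every delay in days 30-60 and a tripled early hazard. The confidence interval 0.65-0.87 of the cited real-world study implies a standard error of ln(0.87/0.65)/3.92 = 0.074 on the log scale. A ratio of 0.965 is then 0.0356/0.074, about 0.5 standard errors. The answer is that the shift is systematic and shared by every listed analysis, while checking for it is cheap.

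**The 60-day rule has other effects.** This also stands. Patients who add another agent within the window leave AI alone, and some may add palbociclib because they are doing badly. Either can favour AI alone. An illustrative simulation (true ratio 1, 30% late, unmeasured prognosis, assumed rates) gave day-0 ratios of 1.02 and 1.03 in these two situations, and day-60 landmark ratios of 1.05 and 1.06. So a landmark is not a cure, and its recovery of 1.00 above depends on delay being unrelated to prognosis.

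**Protocol 9.9 already admits misclassification by the claims algorithm.** This is partial cover. The sentence is generic and does not say that this error has a direction.

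**Table 5-2 allows 60 days for all agents, the appendix footnote 30 days except for CDK4/6 inhibitors.** Those passages need reconciling, but both give palbociclib 60 days.

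**Conclusion.** The point holds in conditional form. To the extent that palbociclib is filled after the first AI fill, the primary hazard ratio contains an immortal-time component favouring palbociclib, and no analysis in SAP 7.6 would reveal it. Confidence is high for the direction of that component only. Under the assumptions stated, with uniform delays over 60 days, the apparent ratio for a true 1.00 is 0.995-0.965 with a flat hazard and 0.986-0.912 with a tripled early hazard. With no late fills it is 1.00.

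A reader might infer more, and the documents do not support it:
- **That the bias would explain a result such as the cited 0.76.** No row of the table comes near that value, and the inputs that decide the size are not in the documents.
- **That the primary estimate is biased towards palbociclib overall.** Other effects of the 60-day rule, unmeasured confounding and later switching could oppose this component, so the net direction is open.
- **That the landmark should replace the primary analysis.** It would change the declared estimand to survival given 60 days alive, and it does not handle prognosis-driven changes in days 0-60.

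This is a cheap improvement, not a reason to discard the planned analysis.

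**What to change.** Keep the day-0 sIPTW analysis as primary. Before any outcome analysis:

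1. In SAP 7.6, commit to (rather than permit) a day-60 landmark sIPTW analysis: patients alive and under follow-up at day 60, arm set by fills to day 60, OS counted from day 60, propensity score refitted on that cohort.
2. Add a supporting day-0 analysis with palbociclib as a time-varying exposure over days 0-60.
3. Report the time from first fill to palbociclib fill in the palbociclib + AI arm, and deaths and censorings by day 60 in each arm. The fill gaps will show whether the issue matters: if nearly all are zero, the component is negligible.
4. Name immortal time among the limitations in Protocol 9.9.

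The cost is wording and some programming, with no new data. The landmark describes only 60-day survivors. It loses about 3-9% of patients to early death under the assumed hazards, plus early disenrolments and moves to an HMO: about 0.5-2% if these run at an assumed 0.25-1% per month (1.971 × 0.25% = 0.5%; 1.971 × 1% = 2%). It is a check on the primary result, not a substitute for it.
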